THE ROLE OF VITAMIN D IN CONTROLLING AND REDUCING DM RISKS (D4D)

Version IV November 2018

SYNOPSIS

Protocol title: The Role of Vitamin D in Controlling and Reducing DM Risks (D4D)

Protocol version: Version IV

LIST OF INVESTIGATORS

Principal Investigator: [name]

Signature: Date:

Organisation: School of Life Sciences, University of Technology, Sydney Address: School of Life Sciences, University of Technology, Sydney

[contact]

Email: [contact]

Co Investigator: Associate [name]

Signature: Date:

Organisation: School of Life Sciences, Program Director, School of Medical and Molecular

Biosciences, University of Technology, Sydney

Address: School of Life Sciences, Program Director, School of Medical and Molecular Biosciences,

University of Technology, Sydney [contact]

Email: [contact]

Co Investigator: Adjunct [name]

Signature: Date:

Organisation: School of Life Sciences, University of Technology, Sydney Address: Specialist Medical Services, [name]

Email: [contact]

Summary

Study title The Role of Vitamin D in Controlling and Reducing DM Risks (D4D)

Protocol version

Version IV

Objectives

To determine if vitamin D can benefit DM and the impacts from different heterogeneous vitamin D sources.

Study design

The D4D trial is designed as a multi-centre, single-blind, randomized, parallel group, superiority study to determine the role of Vitamin D from the oral supplement, sun exposure and dietary invention in controlling and reducing DM risks.

Planned sample size

120-140 participants

Selection criteria

1) Aged ≥ 18 years old; 2) Diagnosed with DM in the preceding 12 months, and not on diabetic medication or insulin treatment; 3) Serum 25OHD is between 28 nmol/l and 85 nmol/l and not on vitamin D supplements or any relevant medications; 4) Do not have thyroid diseases, liver impairment, renal failure, cancer, osteoporosis, dementia, mental diseases or taking relevant medications; 5) Not pregnant or breastfeeding women.

Study procedures

Eligible participants will be randomized in equal proportion into one of 4 groups: vitamin D supplement, dietary intervention, sun exposure and wait list control.

The vitamin D supplement group will be given an oral vitamin D supplement to ingest, dosage set as 500 IU per day. The dietary intervention group will be asked to follow a 'vitamin D food resources' list to obtain 10-15 μ g/d of vitamin D from food. The sun exposure group will be required to expose about 15% of body surface (hands, face and arms) to natural sunlight anytime from 10am to 4pm for 3-4 minutes/d from December to January, or 8 minutes/d from July to August or 10— 11 min/d from February to June or September to November, to get approximately 12.5 μ g/d of vitamin D per day. No interventions will be given to the wait list control group.

The total study period of the trial is 9 months. A face-to-face adherence reminder and examination session will occur at baseline and on a monthly basis. A blood test of vitamin D level and DM biomarkers will be obtained at baseline, and at the 3rd month and 9th month session. Participants who report with any side effects or upset symptoms will be assessed by study therapists and excluded from the trial once being confirmed.

Statistical considerations

Sample size calculation: By setting the significance level α =0.05, the power 1- β = 0.8 based on Campbell & Machin (1993) formula: m=(Z α + Z2 β)2{ π 1(1- π 1)+ π 2(1- π 2)}/ δ 2, (Z α + Z2 β)2 = 7.849, δ = π 2- π 1=0.7-0.35= 0.35; m=28. Therefore for the current study, the sample size of each group is calculated as at least 28, hence it requires at least 112 participants in total. With the consideration of a dropout rate 10%-20%, it is planned to recruit 31-34 participants per group with 123-134 participants in total.

Analysis plan: Data are expressed as means ± SDs. Initially, the Kolmogorov–Smirnov goodness-of-fit test will be used to assess the normal distribution of variables. Secondly, two-factor repeated-measures analysis of variance (ANOVA) will be used with Bonferroni correction in the current trial with time stages and

interventions as factors. A Tukey's post-hoc comparison will be applied to identify the differences between four intervention groups at 3 months and 9 months in the case of significant interaction findings in the ANOVA. Thirdly, correlations between variables were evaluated by using either Pearson (r) (for data with normal distribution) or Spearman (rs) (for data with no normal distribution) correlations. A p-value <0.05 is considered statistically significant. All statistical analyses will be computed using the Statistical Package for Social Science version 17 (SPSS, Chicago, IL, USA). Missing values are treated according to the last observation carried forward (LOCF) method and will be assessed via a sensitivity analysis.

Study duration

The whole study period including research preparation, participants recruitment, intervention, report writing is designed as 3 years; participants are required to be involved in current research for 9 months.

1.	BACKGROUND	6
1.1.	DISEASE BACKGROUND*	6
1.2.	RATIONALE FOR PERFORMING THE STUDY*	6
2.	STUDY OBJECTIVES*	6
2.1.	Primary Objective*	6
2.2.	SECONDARY OBJECTIVES	7
3.	STUDY DESIGN*	7
3.1.	Design*	7
3.2.	STUDY GROUPS	7
3.3.	NUMBER OF PARTICIPANTS*	7
3.4.	NUMBER OF CENTRES	7
3.5.	DURATION	7
4.	PARTICIPANT SECTION	7
4.1.	Inclusion Criteria*	7
4.2.	EXCLUSION CRITERIA*	7
5.	STUDY OUTLINE*	7
5.1.	STUDY FLOW CHART	7
5.2.	Investigation Plan*	9
5.3.	STUDY PROCEDURE RISKS*	11
5.4.	RECRUITMENT AND SCREENING*	11
5.5.	Informed Consent Process*	11
5.6.	ENROLMENT PROCEDURE*	11
5.7.	RANDOMISATION PROCEDURE	11
6.	SAFETY*	12
6.1.	Adverse Event Reporting*	12
6.2.	EARLY TERMINATION	12
7.	BLINIDING AND UNBLINDING	12
8.	STATISTICAL CONSIDERATIONS*	12
9.	CONFIDENTIALITY AND STORAGE AND ARCHIVING OF STUDY DOCUMENTS*	13
10.	OTHER STUDY DOCUMENTS	13
11.	REFERENCES*	14

Version IV; November2018

1.BACKGROUND

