2.2. SECONDARY OBJECTIVES

To determine the prevalence of vitamin D deficiency among T2DM patients and, To determine the differences of heterogeneous vitamin D sources and its impact on DM control.

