3.4. NUMBER OF CENTRES

Participants are to be recruited primarily from the Earlwood Medical Centre (EMC), which is a community medical centre located in south central Sydney. Participants are also to be recruited from the Bangor Medical Centre located in south Sydney. All the following research visits including assessment and data collection will only be conducted in the Earlwood Medical Centre.

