3.5. DURATION

The D4D research is planned to commence in late-2018 and expected to complete by 2021. The participants will be involved during the intervention phase for 9 months. The expected duration of the recruitment phase is 10-12 months.

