5. STUDY OUTLINE*

5.1. STUDY FLOW CHART

Participants screening & recruitment

Complete consent

Randomisation

A. Vitamin D
Supplement
Take the vitamin D
supplement 500 IU/d

B. Dietary intake
Follow the
prescribed dietary
plan to obtain 10-15
µg/d of vitamin D

C. Sun exposure

Expose about 15% of body surface (hands, face and arms) under the sun anytime from 10am to 4pm for 3-4 min/d from December to January, or 8 min/d from July to August or 10–11 min/d from February to June or September to November. This will provide approximately 12.5 µg/d of vitamin D

D. Wait list Control Nil intervention

Baseline assessment

- Information delivery session
- Problem and strategy session
- Anthropometry assessment for all: weight, height, BMI, waist & hip ratio
- Blood test (HbA1c, BSL, insulin and serum 25 OHD)

Monthly follow up session

- Anthropometry assessment for all: weight, BMI, waist & hip ratio
- Supplement group: pill count
- Diet group: collect data from smartphont application or paperbased diary
- Sun exposure group: collect data from sun exposure questionnaire
- Adherence assessment
- Problem and strategy assessment

3rd month assessment

- Anthropometry assessment for all: weight, BMI, waist & hip ratio
- Supplement group: pill count
- Diet group: collect data from smartphont application or paperbased diary
- Sun exposure group: collect data from sun exposure questionnaire
- Adherence assessment
- Problem and strategy assessment
- Blood test (HbA1c, BSL, insulin and serum 25 OHD)

Monthly follow up session: As above

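### From about mid-April to September the sun arm's fixed minutes give much less vitamin D late in the 10am–4pm window than at midday, yet one dose is stated for the whole window

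*Protocol*

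**What the plan says.** The Synopsis tells the sun group which skin to uncover (arms, face and hands) and when: "to natural sunlight anytime from 10am to 4pm for 3-4 minutes/d from December to January, or 8 minutes/d from July to August". The remaining months get 10–11 "min/d from February to June or September to November, to get approximately 12.5" µg/d. The flow chart in Section 5.1 repeats the window ("under the sun anytime from 10am to 4pm for 3-4 min/d from December to January") and adds, without qualification, "This will provide approximately 12.5" µg/d. Nowhere do the minutes depend on the hour.

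The diet group follows a food "list to obtain 10-15" µg/d, and the supplement group takes 500 IU/d. Section 5.3 describes 500 IU as the dose delivered by all three routes. Section 2.2 makes it a secondary objective to determine "the differences of heterogeneous vitamin D sources and its impact on DM control".

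The main recruiting centre is "located in south central Sydney" (Section 3.4). Section 3.5 states: "The participants will be involved during the intervention phase for 9 months".

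Section 5.2 promises sun-group instructions that cover timing and weather, together with a daily exposure diary, and it mentions a noon outing as an example of an adherence strategy. Neither item narrows the permitted window.

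**The concern.** The protocol varies the minutes by month, so it treats the strength of the sun as determining the dose. It then leaves the hour free over six hours. In the cooler months, on Sydney standard time, the sun at 4pm is low, and equal minutes on equal skin should produce less vitamin D than at midday. A participant who always goes out at 4pm in June is fully adherent but receives a much smaller dose than one who goes out at noon.

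What is at stake is mainly the comparison of sources. For habitual late-afternoon participants, a weaker 25OHD or HbA1c response could reflect the hour they chose and not sunlight as a source. Any nine consecutive months leave out three, so they include between 6 − 3 = 3 and 6 of the six April–September months. Everyone who completes the sun arm passes through the affected season.

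**Working it through.** **The plan's own figure.** 12.5 µg/d agrees with the supplement dose (500 IU ÷ 40 IU per µg = 12.5 µg). It cannot be rebuilt from the prescribed minutes, because the protocol gives no UV intensity, skin type or minutes-to-µg rate. The check therefore uses ratios within a month, in which minutes, skin area and conversion rate cancel.

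**Inputs from the protocol.** Window 10am–4pm; minutes 3–4 (Dec–Jan), 8 (Jul–Aug), 10–11 (other months); location Sydney.

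**Assumptions.** Latitude 33.9° S, longitude 151.1° E; clock time with daylight saving from October to early April (2019 changes); clear sky; 15th of each month; dose per minute proportional to sin(elevation).

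**Formula.** sin(el) = sin(lat)·sin(dec) + cos(lat)·cos(dec)·cos(hour angle), with the equation of time, evaluated each minute from 10:00 to 16:00. In all six months below the lowest value falls at 16:00.

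| Month | sin(el), highest | sin(el), 4pm | Ratio | Ratio, square root | Ratio, squared | 10am–2pm spread |
|---|---|---|---|---|---|---|
| Apr | 0.728 | 0.305 | 2.38 | 1.54 | 5.7 | 1.19 |
| May | 0.606 | 0.189 | 3.21 | 1.79 | 10.3 | 1.25 |
| Jun | 0.541 | 0.148 | 3.65 | 1.91 | 13.3 | 1.25 |
| Jul | 0.568 | 0.185 | 3.07 | 1.75 | 9.4 | 1.23 |
| Aug | 0.673 | 0.269 | 2.50 | 1.58 | 6.3 | 1.19 |
| Sep | 0.808 | 0.361 | 2.24 | 1.50 | 5.0 | 1.19 |

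Ratios use unrounded sines. The square root stands in for a flatter response (upright skin) and the square for a steeper one (more UV absorbed at low sun). Slightly different Sydney coordinates move June to 3.67, and to 13.5 when squared. The first days of April, still on daylight saving, give only about 1.44, hence mid-April.

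**Where in the window.** Midday to 3pm is 1.50–1.76 in these months, and midday to 10am only 1.13–1.23. The problem is the late end.

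**Arm mean.** If hours are spread evenly over the window, the mean dose is 81–85% of the midday dose. Were the minutes calibrated to midday, that would be 12.5 × 0.81 = 10.1 to 12.5 × 0.85 = 10.6 µg/d.

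**Effect of a 10am–2pm limit.** The spread falls to 1.19–1.25 on the linear model, and to at most 1.25² ≈ 1.6 on the squared one.

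**October–March.** Within a month the hour-of-day spread is smaller (1.32–1.47). Between months, however, minutes (midpoints 3.5 and 10.5) times highest sin(el) gives, in relative units: Oct 9.6, Nov 10.2, Dec 3.4, Jan 3.4, Feb 9.8, Mar 9.0. The midday dose therefore differs about 3-fold (10.2 ÷ 3.4 = 3.0), because the minutes fall to 3–4 while the sun barely changes.

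**The case against.** The strongest case against is that the protocol offers no UV data, so everything rests on an imported model whose ratio runs from 1.5 to 13.5 with the exponent chosen. On the flatter response April, August and September give only 1.50–1.58. That stands, and it is why the size is given as a range. All three versions still show a deficit at 4pm.

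A reader might infer that the stated dose is impossible, by testing the sun arm against the diet arm's 10–15 µg/d. The documents do not support this. That band is a dietary target, not a sun-arm tolerance; the sun dose is only approximate; and on the flatter response half the months lie close to a 1.5-fold spread.

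A reader might also infer that October–March is in order because the hour matters less then. The 3-fold change in midday dose between those months, on the same model, argues against that. It also shows that narrowing the window will not by itself deliver 12.5 µg/d.

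Part of the matter may be handled elsewhere. The timing instructions have content that is not shown, the questionnaires are separate documents, and the diary may already capture clock time. Serum 25OHD at baseline, 3 and 9 months would show a weak response, but without clock times it could not show whether the hour was the cause. Flexible hours may also help adherence.

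**Conclusion.** The concern holds in a limited form. One dose is attached to fixed minutes across the whole window, and from about mid-April to September that dose is unlikely to hold in late afternoon. The shortfall at 4pm relative to midday is about 2.2–3.7-fold on the linear elevation model, 1.5–1.9 if the response is flatter and 5–13.5 if steeper, given Sydney coordinates, clear sky and clock time as assumed.

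The consequence is modest. It falls mainly on the secondary comparison of sources, for participants who habitually go out late, and the protocol does not say how many that would be. It would be going too far to conclude that the arm as a whole is under-dosed or that the primary comparison with wait-list control is compromised: evenly spread hours cost only 15–19% of the midday dose, and no absolute dose at any hour can be derived from the document. This is a low-cost improvement to consider, held with medium confidence.

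**What to change.** In the Synopsis and Section 5.1, limit sun exposure from April to September to about 10am–2pm, and carry the same limit into the timing instructions of Section 5.2, so that the noon suggestion there becomes part of the prescription. Have the existing sun diary record start clock time as well as minutes, if it does not already, so that the hour can be examined when sources are compared.

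The cost is a wording change in the protocol and participant instructions, perhaps one diary column, slightly more recording, and less flexible hours in the cooler months. The change removes most of the hour-of-day variation. The basis of the monthly minutes is a separate matter that it leaves untouched.

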5.3. STUDY PROCEDURE RISKS*

Adverse events will be collected after the participant has provided consent and enrolled in the study. In the current trial, the dosage of vitamin D (500 IU) provided through supplementary, dietary or sun exposure is considered to be safe and it is unlikely to cause adverse effects. However, if participants report with any adverse effects, they will be provided with medical treatment if necessary and excluded from the trial.

Other than that, there is the possibility that in the dietary intervention group, some subjects may report with food intolerance and allergy symptoms to seafood or dairy products. Research staff will record the incidences. Participants will be asked to attend a dietitian review for appropriate suggestion to minimize the risks. If the adverse effects are continued, participants will be excluded from the trial, related test or medical treatment will be provided if necessary.

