6.1. ADVERSE EVENT REPORTING*

Adverse event

Adverse events will be collected after the participant has provided consent and enrolled in the study. In the current trial, the dosage of vitamin D (500 IU) provided through supplement, dietary or sun exposure is considered to be safe and it is unlikely to cause adverse effects. However, if participants report any adverse effects, they will be provided with medical treatment if necessary and excluded from the trial.

In addition, there is the possibility that in the dietary intervention group, some participants may report food intolerance and allergy symptoms to seafood or dairy products. Research staff will record the incidence. Participants will be asked to attend a dietitian review for appropriate suggestions to minimize the risk of further food intolerances/allergies. If the adverse effects continue, participants will be excluded from the trial and provided with relevant test and medical treatment if necessary.

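### The sun-exposure minutes cannot give a constant 12.5 µg/d in Sydney: July-August gets fewer minutes than February or November

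*Protocol*

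**What the plan says.** The sun-exposure schedule stands in the synopsis (study procedures) and again in the Section 5.1 flow chart, with the same minutes:

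| Months | Minutes per day |
|---|---|
| December-January | 3-4 |
| February-June and September-November | 10-11 |
| July-August | 8 |

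The synopsis prescribes "3-4 minutes/d from December to January, or 8 minutes/d from July to August", and for the remaining months 10 to "11 min/d from February to June or September to November". Exposed skin (roughly 15% of the body) and the permitted hours (10am to 4pm) do not change over the year. Both places claim one dose for the whole schedule: the synopsis has "min/d from February to June or September to November, to get approximately 12.5" µg/d, and the flow chart has "min/d from February to June or September to November. This will provide approximately 12.5" µg/d.

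Section 3.4 puts all study visits at the Earlwood centre, "which is a community medical centre located in south central Sydney", so the seasons are those of the southern hemisphere. Sections 5.3 and 6.1 treat the three active routes as one dose; Section 5.3 reads "the dosage of vitamin D (500 IU) provided through supplementary, dietary or sun exposure is considered to be safe", and Section 6.1 is nearly identical. Section 6.2 again says that this dose level is obtained through sun exposure. One secondary objective (Section 2.2) is "To determine the differences of heterogeneous vitamin D sources and its impact on DM control".

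**The concern.** With skin area and hours fixed, only the strength of the sun can offset a change in minutes. A constant dose therefore needs the fewest minutes in midsummer and the most in midwinter, with the months beside midsummer close to the summer value. The schedule does otherwise. February and November, which adjoin December-January, get about three times the midsummer minutes. July and August then get fewer minutes than February and November. June and July, adjacent winter months, fall in different bands.

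At stake is what the sun arm tests. The protocol treats it as 12.5 µg/d, equal to the 500 IU supplement. If the dose is something else and changes with the calendar, a difference between sun and supplement, or sun and diet, cannot be separated into an effect of source and an effect of dose.

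**Working it through.** **Target.** 500 IU ÷ 40 IU per µg = 12.5 µg. The target agrees with the supplement dose; the problem is the minutes.

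**Step 1: protocol figures only.** Yield per minute implied by 12.5 µg/d = 12.5 ÷ minutes.

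- December-January: 12.5/4 = 3.13 to 12.5/3 = 4.17 µg/min
- July-August: 12.5/8 = 1.56 µg/min
- February-June and September-November: 12.5/11 = 1.14 to 12.5/10 = 1.25 µg/min

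Ratios that a constant dose requires:

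- July-August sun against February or November sun: 10/8 = 1.25 to 11/8 = 1.375
- December sun against November sun: 10/4 = 2.5 to 11/3 = 3.67

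The first ratio has the wrong sign for Sydney, since it makes the winter sun the stronger. Even if July sun were as strong as November sun, 8 minutes would give only 8/11 = 73% to 8/10 = 80% of the November dose. This step needs no UV model.

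**Step 2: illustration of size.** The protocol gives no UV figures, so these are assumptions: latitude 34° S; mid-month solar declination = −23.44° × cos(2π(day + 10)/365); yield per minute proportional to sin(solar elevation)^k, with k from 1 to 2.4; and 3.5, 8 and 10.5 minutes for the three bands.

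Noon elevations are December 79.3°, November 75.1°, February 69.4°, August 42.1°, July 34.5° and June 32.7°.

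| Yield per minute at noon | k = 1 | k = 2.4 | Schedule needs |
|---|---|---|---|
| July ÷ February | 0.60 | 0.30 | 1.25-1.38 |
| July ÷ November | 0.59 | 0.28 | 1.25-1.38 |
| August ÷ February | 0.72 | 0.45 | 1.25-1.38 |
| August ÷ November | 0.69 | 0.42 | 1.25-1.38 |

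Monthly dose is minutes × sin(elevation)^k. Averaging it over consecutive months from each possible start month gives these ratios of highest to lowest:

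| Period | Noon, k = 1 | Noon, k = 2.4 | 10am-4pm average, k = 1 | 10am-4pm average, k = 2.4 |
|---|---|---|---|---|
| First 3 months (September against June start) | 1.81 | 3.24 | 1.93 | 3.61 |
| All 9 months (September against December start) | 1.23 | 1.44 | 1.25 | 1.47 |

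Single months at noon differ 2.97-fold (k = 1) to 4.74-fold (k = 2.4). At the stated minutes kindest to the protocol (10 in November, 4 in December), November still gives about 2.4 times December's dose, which "approximately" does not cover.

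**Step 3: anchoring at midsummer.** Suppose 3.5 minutes in December-January does give 12.5 µg. A separate calculation (latitude 33.9° S, exponents 1 to 3, noon and window averages) gives:

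| Month | Minutes needed for 12.5 µg | Dose from the scheduled minutes (µg/d) |
|---|---|---|
| November | 3.5-3.7 | about 36-37 |
| February | 3.7-4.1 | 32-36 |
| July | 6.0-21.8 | 5-17 |
| August | 5.1-12.6 | 8-20 |

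In every scenario July and August need more minutes than February and November. None of the exponents makes the scheduled dose constant.

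**The case against.** The ordering is hard to defend; the serious objections concern weight.

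- **The primary comparison is unbiased.** Sun exposure against wait-list control on HbA1c is randomised and the arms enrol concurrently. This stands.
- **Nine months of treatment smooth the dose.** The 1.23- to 1.47-fold spread is no wider than the 10-15 µg/d (1.5-fold) that the protocol allows the diet arm. This stands for relative spread at 9 months. It does not show that the average is 12.5 µg/d, and it does not help at 3 months.
- **The 3-month ratios are extremes.** They compare the most and least favourable start months. Section 3.5 plans 10-12 months of recruitment, so the arm mean averages over start months. This also stands: the ratios describe variation between participants within the sun arm, not a shift of the arm mean. The single-month ratio matches no blood test.
- **The winter minutes are not the only fault.** At k = 1 the lowest monthly dose falls in January, because of the drop to 3-4 minutes. This is correct, and it is why the protocol cannot show which band is wrong.
- **Exposure and response are recorded.** Sun diaries are kept, and 25OHD is measured at baseline, 3 and 9 months. That shows what was achieved but does not make the prescribed dose correct.
- **The 500 IU statements concern safety, and no objective demands equal doses.** This is fair, but they rest on the same equivalence, and without it a source difference cannot be told from a dose difference.

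**Conclusion.** The concern holds. The schedule cannot deliver the same vitamin D dose in every month in Sydney. That conclusion rests only on the stated minutes, the unchanged skin area and hours, and the southern-hemisphere seasons, and it is held with high confidence. The fold-differences are illustrations that depend on the assumed latitude, exponent and time of day.

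The consequence is moderate. The primary randomised contrast is not biased, but the sun dose it tests is ill-defined. The secondary comparison of sources loses its claimed dose equivalence for the sun arm, and the 3-month assessment is more exposed than the 9-month one. The correction should be made, but the error does not invalidate the trial.

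**What to change.** Before sun-arm participants are instructed, do one of the following.

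1. **Reset the minutes** in the synopsis and Section 5.1 from one cited UV-to-dose source. They should rise from midsummer to midwinter, with February and November near the summer value and June-July longest. The information-session instructions (Section 5.2) must match.
2. **Withdraw the dose claim.** Keep a schedule, delete the 12.5 µg/d figure for the sun arm in the synopsis and Section 5.1, and take sun exposure out of the 500 IU statements in Sections 5.3 and 6.1 and the similar wording in Section 6.2. State that differences between sources will be interpreted alongside the change in 25OHD achieved in each arm.

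Either is one short amendment, with no new data collection and no change to the analysis model. The first also needs a UV source, which the protocol does not now contain, and it changes what participants are told to do; the second changes only wording.
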